6.0 Procedures Involved*

6.1 We plan to recruit 175 parent/child dvads, high in error sensitivity (measured with self-report), and randomize 150 to an intervention condition (50 to parent/child, 50 to parent only, 50 to child only) and 25 to an active control condition. We plan to utilize an unbalanced design (150 intervention versus 25 controls) due to the fact that longitudinal data in developmental samples suggests the ERN is typically stable or increases across development. Therefore, a decrease in the ERN is not expected to occur in the control group. We will measure the ERN in children pre and post intervention, as well as error sensitivity and anxiety symptoms. At a six-month follow-up, we will again assess children's ERN, as well as error sensitivity and anxiety symptoms. We chose a six-month follow-up assessment to allow for adequate time for the parenting intervention to impact children (1-month may be too brief to observe impact), as well as to allow for children and parents to access the additional online materials (24 modules will be offered). This time was also selected to minimize drop-out that might occur over longer follow-up periods.

Further, before and during all in-person lab visits, we plan to take protective measures in order to reduce any possible spread of COVID-19 and to prevent any individuals at higher risk from participating in our study. Provided IRB approval, we plan to resume lab visits on August 1 with these protective measures in place.

6.2 Year 1: intervention development, collect pilot data from 10 parent/child dyads.

Year 2 - 4: recruit and collect data from 6 parent/child dyads per month, total N = 175 parent/child dyads. We will also collect 6-month follow-up data in the lab for each parent/child dyad.

Year 5: complete all follow-ups. Data processing, analysis, statistical procedures and manuscript preparation.

Risks are fairly minimal. There is a chance that some parents or children may experience mild, transient distress during parts of the assessments. All questions (self-report) are the type typically asked during a routine psychological or medical evaluations. If necessary, the assessment can be interrupted or terminated. The family (parent and patient) will be clearly informed that they are free to terminate participation at any point in the protocol.

Upon scheduling their visit, subjects will be asked a series of questions to determine if they or anyone in their immediate family is at higher risk to being exposed to Coronavirus. Individuals who meets these criteria will be excluded from participation in the study. These questions will include:

1. "Are you or anyone in your immediate 65 years of age or older?"

2. "Do you, or anyone in your immediate family, have a serious medical condition such as diabetes, heart, lung, kidney, or liver disease, or severe obesity?"

3. "Do you or anyone in your immediate family have poor immunity due to cancer treatment or other conditions involving weakened immune systems?"

Prior to their in-lab visit, subjects will receive a phone call from research personnel updating them on the steps being taken to reduce the risk of Coronavirus transmission. On the day of each in-person lab visit, subjects will be called and asked an additional series of screening questions in order to see who may have been exposed to Coronavirus. Individuals who meets these criteria will be excluded from participation in the study. The screening questions and script to be used are as follows:

"In the past 14 days, has your family:

1. Traveled outside of the Tallahassee area?

2. Had flu-like symptoms such as cough, low-grade fever or high temperature (100.4°F), shortness of breath, and/or difficulty breathing?

3. Been in contact with a person who has flu-like symptoms or a person with suspect, probable or confirmed coronavirus (COVID-19)?

4. Been to a nursing home or state hospital?"

The EEG and startle recording is completely non-invasive. The EEG will be recorded with an ActiveTwo EEG recording system, which does not require abrading the skin. There is the possibility that some participants will experience mild, temporary itching or tingling sensation in response to the electrode cap or electrode gel.

Informed consent and assent will be obtained prior to participation, and risks will be explained carefully to the participants' parent. All information with identifying information collected during the project will be kept in a locked storage cabinet to which only [name] and the study coordinator will have access. All data will be stored separately from identifying information and will be password protected. No names will be maintained in data records; rather, information will be coded by ID numbers only. Each individual will receive a unique I.D. number thereby allowing handling of data on all subjects without using individual names. PI [name] will be responsible for monitoring the maintenance of confidentiality. In the event of a breach of confidentiality, he will inform the subject and his/her parents that the breach occurred; any breaches of confidentiality will be reported to the Institutional Review Board. Codifying participants by unique identifiers is an extensive practice that is highly efficient at protecting anonymous participation. No individual child or family will be identified in any publications or presentations of the research findings.

Upcoming procedures are repeatedly explained to the children and their parent, giving them a sense of control over what is happening in their environment. Rather than closed yes/no questions, open-ended questions with regard to comfort and well-being will be used throughout the procedures to give subjects the

opportunity to voice any concerns or discomfort. Subjects will also be given the opportunity to ask questions regarding the research procedures at any time during the protocol.

Although we don't expect it frequently, some subjects may endorse suicidality or increased risk for suicidality; in this event, safety assessments will be conducted and, when necessary, appropriate consultation with [name] will be held to determine disposition. [name] is a clinical psychologist, with an office on the same floor where the research will take place. In the event that a participant is in imminent danger to themselves, their parents will be informed. The participant and [name] will meet with the subject and their parent to establish a safety plan – which may include transporting the child to the emergency room for further psychological evaluation or a referral for follow-up evaluation with an outside provider. Referrals will be on hand and can be provided. We will use validated procedures for suicide assessment, specifically the structured interview recommended by Joiner et al. (1999) & Chu et al. (2015), and use the following method to designate risk severity (refer to ABHC Suicide Risk Assessment form for detailed information on the assessment):

1. An individual's risk for suicide is designated nonexistent if he or she has no current suicidal symptoms, no history of suicide, and no or few other risk factors.

2. Risk for suicide is considered mild if the individual is a multiple attempter with no other risk factors or is a non-multiple attempter experiencing suicidal ideation of limited intensity and duration, no or mild resolved plans and preparation, and no or few other risk factors.

3. An individual is designated at moderate risk if he or she is a multiple attempter with any other significant risk factor. A non-multiple attempter with moderate to severe resolved plans and preparations or moderate to severe suicidal desire and ideation accompanied by at least two other risk factors is also considered to be at moderate risk for suicide.

4. A multiple attempter with two or more risk factors or a non-multiple attempter with moderate to severe symptoms of resolved plans and preparations accompanied by one other risk factor is designated at severe risk for suicide.

5. An individual is at extreme risk for suicide if he or she is a multiple attempter with severe resolved plans and preparation or is a non-multiple attempter with resolved plans and preparations and two or more other risk factors.

Once an individual has been assessed for suicide risk, we will take the following actions, as suggested by Joiner et al. (1999) and Chu et al. (2015):

In addition, if children and/or their parents endorse experiencing significant psychological distress (e.g., significant anxiety or depression) during any portion of the study, the participants will be offered referral information for psychotherapy and/or pharmacologic treatment at Florida State University and the surrounding community. Participants who are initially enrolled in the study

will not be excluded from completing study procedures if they begin receiving treatment during the study. Because information relating to child abuse may be assessed, the staff will follow federal and state child abuse reporting requirements. Participants will be informed of the need to report child abuse prior to eliciting this information. In case of any reported abuse by the child or parent, the parents will be informed about the federal mandated reporting laws, verbally and in writing. In cases where it is necessary to make a child abuse report, the family will always be informed prior to contacting any state agency, and given the option of making a self-referral to protective services.

6.3 EEG, self-report, observational video data, and clinical interviews will be collected.

Self-report. The current proposal will utilize dimensional measures of anxiety symptoms measured by the Screen for Child Anxiety Related Emotional Disorders (SCARED) questionnaire. Both the parent and child will complete the SCARED regarding anxiety symptoms experienced by the child before and after the treatment at the baseline assessment, and at the follow-up assessment.

To capture a broad spectrum of symptoms, we will also administers the Child Behavior Checklist (CBCL) at the baseline and follow-up assessment. The CBCL is a 113-tiem parent-report checklist that assesses emotional and behavioral problems (internalizing and externalizing) over the past 6 months. We will utilize the depression scale from this measure, as well as the obsessive compulsive scale.

Additionally, to assess error sensitivity in children, we will use our previously validated measure (i.e., the Child Error Sensitivity Index), before and after the intervention, and at follow-up. This measure includes 9 items indexing error sensitivity, for example: "I feel upset when other people don't like something I have done", "If I make a mistake, I always want to fix it", and "When I make a mistake, I feel anxious", and has good psychometric properties.

We will also assess parent's sensitivity to their child's errors before and after the intervention, and at follow-up. Our measure of Parent Sensitivity to Children's Errors includes 20 items, such as the following: "When I notice a mistake my child made, I feel upset", "If my child makes a mistake, I have a strong urge to fix it immediately", "When my child makes a mistake, I feel anxious", "I like to watch my child do things to make sure she/he doesn't make mistakes."

Additional self-report measures include the following (all will be uploaded under documents section):

Child:

Child and Adolescent Perfectionism Scale CRPBI CASI Child report: parent sensitivity to my errors Acceptability Measure

Parent:

IDAS Parent ASI to child Parent ASI FASA Parent report on child's error sensitivity Parent sensitivity to child's errors Parent error sensitivity Avoidance questionnaire CBQ PSDQ CRPBI Acceptability Measure Child Anxiety Life Interference Scale – Preschool Version (CALIS-PV) Coping with Children's Negative Emotions Scale (CCNES) Spence Preschool Anxiety Scale (Parent Report)

Observational behavioral task. We will also use a lab-based observational task to measure error sensitivity in children, as well as parent's sensitivity to their children's errors, before and after the intervention, and at the follow-up lab visit. These will be tasks that we have utilized in a previous study at FSU in this same age-range.

Episode 1: Guessing Card Game (Headbands).

"For this game, you will each wear one of these headbands. (demonstrate and then help participants get headbands on their head) You are each going to be given 10 cards. Please do not look at your cards. You will take turns guessing your own cards. When it is your turn, take the card from the top pile and put it in your headband, like this (demonstrate). You should NOT look at your card when you do this. You will ask questions to your partner to guess what your card is. Your questions can be things like: Am I an animal? Do I have feathers? Am I a thing? Am I a food? You cannot ask: What is my card?, but you can ask pretty much anything else. When you correctly guess your card, then you put the card face up in a pile and switch turns. Your goal is to correctly guess as many cards as possible before your time is up. Do you have any questions?" Make sure parent and child have headbands on and have a pile of 10 cards each. Then tell the participants they can start and make sure to start the 3 minute timer and record the episode .

When timer goes off, enter the room and tell the family that they did a great job and that now it is time to start a new activity.

Episode 2: **Drawing while taking turns.**

"For this activity, we want you to draw these pictures yourselves. We want you to try to be as accurate as possible. You will take turns drawing. Each of you will only draw one line and then pass the drawing to your partner so that they can draw the next line. You

will go back and forth. Try to get as many completed as you can, while being accurate, within 3 minutes."

Give parent/child the pictures and blank paper and pens (not pencils). Tell the participants that they can start and set the 3 minute timer and record the episode . When timer goes off, enter the room and tell the family that they did a great job and that now it is time to start a new activity.

Episode 3: **Picasso Tiles.**

"For this activity, _____(child's name) will build with the Picasso Tiles, while ______(parent's name) will give directions. We would like you to use the Picasso Tiles to build, as accurately as possible, the design on this picture (point to image). If you finish this, you can move to the next one. We want ______(parent's name) to be looking at the image and giving directions to ______ so that he/she can build the design. Please do not let ______(child's name) look at the picture. We would like you to work together. Do you have any questions?"

Give child the Picasso Tiles and give the parent the images. Tell the participants they can start and set the 3 minute timer and record the episode .

When timer goes off, enter the room and tell the family that they did a great job and that now it is time to start a new activity.

Episode 4: Negative Discussion.

"For this activity, we want you to talk together about a time this week when _____

(child's name) did something wrong. If you can't think of something from this week, you can talk about the most recent situation that you can remember. You will have 3 minutes to have this discussion. Do you have any questions?"

Tell the participants that they can start and set the 3 minute timer and record the episode . When timer goes off, enter the room and tell the family that they did a great job and that now it is time to start a new activity.

Episode 5: Positive Discussion.

"For this activity, we want you to talk together about a time this week when

(child's name) did something right. If you can't think of something from this week, you can talk about the most recent situation that you can remember. You will have 3 minutes to have this discussion. Do you have any questions?"

Tell the participants that they can start and set the 3 minute timer and record the episode . When timer goes off, enter the room and tell the family that they did a great job and that now it is time to start a new activity.

The parent and child will be given directions for each task (which will last approximately 2 - 3 minutes) while being video-taped. The videos will be coded for sensitivity to mistakes (modified from [name] coding schemes). For example, negative or positive statements regarding errors or imperfections will be coded (e.g., I hate making mistakes, I'm bad, I'll never do this right, etc.). After meeting with [name] at her lab for training on this approach, I will train a team of coders (undergraduate assistants) to code these observations reliably and use Mangold coding software to track codes second by second and to do reliability analyses.

EEG task. Children will complete a developmentally appropriate go-no/go task wherein they are instructed to "shoot" aliens when they see them on the screen (by clicking a mouse button) and "save" astronauts by not clicking when they are on the screen. After completing 5 practice trials, children complete 200 trials. Children will complete the go-no/go task before and after the intervention at the first lab assessment, and once at the follow-up lab assessment. We have used this task in children in this same age-range at Florida State University, with no adverse events.

The EEG assesses brain electrical activity through surface recording disks (electrodes) which are placed near the participant's head. The electrodes transmit the signals, which are then amplified and stored on a computer. The procedure is entirely non-invasive. A custom designed 32-electrode Lycra cap will be placed on the participant's head. In order to record the brain's activity, these disks need to be filled will a gel which allows the electrodes to better record brain activity at the scalp. Therefore, the participants in this study will need to clean their hair after participation. The gel is completely water soluble, and the procedure is painless. [name] laboratory has sinks and towels, and the investigators will help to make sure the participant has thoroughly rinsed all the gel from their hair. After an accurate signal is assured, the signal derived from the electrode cap is then amplified, transmitted to a computer, and stored for later analysis. In addition to the EEG recording, muscle activity from around the eyes may be recorded from the subjects. Muscle activity from around the eyes is recorded by small sensors that will be placed above and below the participant's left eye, as well as on the outer canthi (just below the eyebrow) of each eye. These procedures are completely non-invasive and painless.

EEG data processing and analyses. While participants complete the Go/No-Go task, EEG will be recorded from 32 scalp locations. The response-locked ERPs will be averaged separately for each trial type (e.g., correct and incorrect responses), and baseline correction will be performed using the interval from -500 to -300 ms before response commission. Average activity at three electrode sites (FCz, Cz, and Fz) between 0 and 100 ms after the response will be exported for each subject – we have previously shown that this is where the ERN is maximal and most reliable in children 82. In order to obtain a measure of differentiation between errors and correct responses, the average activity on correct trials will be subtracted from the average activity on error trials (i.e., the ERN). Procedure. Research assistants will explain the study to parents and children and obtain consent for participation. Families will be randomized to a group (parent only, child only, parent/child, or control). Parents and children will participate in a brief observational task and complete questionnaires. Children will then complete the go-no/go task. After this, a trained research assistant will guide the child through the computer intervention or control. After the intervention, children will complete the go-no/go task again, and complete the observational task and questions. Simultaneously, parents will be completing questionnaires and will be administered the intervention or control. The first lab assessment will take approximately 2 - 3 hours.

The second lab assessment will take place approximately 6 months later. At this lab visit, both parents and children will complete follow-up questionnaires and behavioral observation. Additionally, children will complete the go-no/go task.

Clinical Interviews. We plan to conduct two clinical interviews with the parent, at each lab visit. Both interviews are assessments we routinely utilize in our research studies at FSU and will be conducted by a research assistant or graduate student who is trained in the administration of these interviews and has demonstrated reliability. We plan to complete the Schedule for Affective Disorders and Schizophrenia for School-Age Children: Present and Lifetime Version (K-SADS-PL: Kaufman, Birmaher et al., 1997) with the parent regarding the child's symptoms. Additionally, we plan to complete the Mini-International Neuropsychiatric Interview (MINI SCID) with the parent regarding the anticipate that these interviews (together) will take approximately 30 - 40 minutes to complete. As in previous studies, the interviews will be audio recorded for the purposes of coding reliability. Participants will be asked if it is ok to record the interview before each interview begins.

6.4 There is no plan for follow-up after the second lab assessment.

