5.0 Study Intervention

Description: As part of the current proposal, during Year 1, we 1.1 plan to develop a computerized intervention to be administered to parents and children separately. All participants in an active condition (parent/child, parent only, or child only) will receive the initial treatment session in the baseline lab visit. Additional materials that expand upon the concepts presented in the 1st session will be available online for children and parents between the baseline and follow-up assessment (depending on condition, e.g., in parent only condition, only parents will have access to between-session materials). These materials will include worksheets, games, and handouts. Participants will be told that participation in these additional online modules is optional and we will send a weekly reminder (via email or text) to remind them of concepts from the initial session, as well as provide the links to the additional materials. We will track utilization of the additional materials in parents and children. Additionally, as part of these additional modules, we will periodically ask parents and children to complete the Error Sensitivity Index to track changes across the 6 months between lab assessments. The development of this intervention, and testing its impact on ERN, is the primary goal of the proposed training grant. [name] is an expert in the area of computerized treatments for anxiety and will aid in the development and implementation of the intervention. Additionally, Drs. [name], [name], [name], and [name] all have expertise in intervention development and I will consult with them regularly during the development phase of the training grant. For the child intervention, we will use developmentally appropriate language, as well as stories that children between the ages of 5 and 7 can understand and relate to. We will train research assistants to guide children through the computer intervention and answer questions when children appear to be confused. We used this approach successfully when administering the Child Error Sensitivity Index to children between the ages of 5 and 7 years-old, as well as during pilot data collection. This intervention will be based on the constructs in the Child Error Sensitivity Index, as well as other constructs, that relate to the ERN – for example, perfectionism, fear of evaluation from others, and over-valuation of the negative consequences of errors. The intervention will focus on basic concepts such as: "making mistakes is how we learn new things", "everybody makes mistakes", and "good things come from mistakes." While the first session will focus primarily on constructs in the Child Error Sensitivity Index, the additional online materials will expand beyond this. For example, we will cover other constructs that may also relate to the ERN: e.g., tolerance of uncertainty, distress tolerance, mindfulness, constructive self-talk, facing fears, identifying sensations of anxiety, avoidance, behavioral inhibition, checking behavior, etc. - all in the context of, or relating to, performance monitoring or error sensitivity. The intervention will be

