10.0 Subject Population*

10.1 Participants in the study will be 175 parent and child dyads recruited using the Family Registry at Florida State University (FSU). I plan to recruit families with children between the ages of 5 and 7 years of age.

- 10.2 We plan to recruit parent/child dyads who are high in error sensitivity (as measured by the Child Error Sensitivity Index, selfreport). Because our intervention will be designed to target error sensitivity, we will recruit families who score at least .5 standard deviations above the mean on the Child Error Sensitivity Index or the Parent Sensitivity to Children's Errors Index. We will derive means and standard deviations from our previous study, which was conducted in this same age-range and community. Additionally, we will request that the primary caregiver accompany the child to the lab visit (i.e., spends at least 50% or more of total parenting time with the child). Prior to the in-lab visit, participants will complete an additional phone screen to determine whether they meet any Coronavirus-specific exclusion criteria. This phone screen will assess whether participants may have contacted Coronavirus and whether they are at higher risk for severe illness. Any participants who do not pass this screening will not be permitted to take part in the study.
- 10.3 This study will not include: adults unable to consent, pregnant women, prisoners. The study will include: children.

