13.0 Recruitment Methods

13.1 Participants in the study will be 175 parent and child dyads recruited using the Family Registry at Florida State University (FSU) or a targeted mailing list. The FSU Center for Developmental Science implements on-going recruitment throughout the Tallahassee community, focusing on children and families. They maintain a database, which includes the names, ages, and contact information of children and families interested in participating in research studies. The Family Registry is comprised of over 1,500 families to date, and continues to grow each week due to regular recruitment events in the community. I plan to recruit families with children between the ages of 5 and 7 years of age. In addition to utilizing the Registry at FSU, I plan to post fliers in the community and recruit families at additional community events.

13.2 Source of recruitment: FSU Center for Developmental Science Family Registry and fliers that will be posted through-out the community. We also plan to utilize a targeted mailing list for children and families in the Tallahassee community.

We plan to recruit parent/child dyads who are high in error 13.3 sensitivity (as measured by the Child Error Sensitivity Index, self-report). Because our intervention will be designed to target error sensitivity, we will recruit families who score at least .5 standard deviations above the mean on the Child Error Sensitivity Index or the Parent Sensitivity to Children's Errors Index. We will derive means and standard deviations from our previous study, which was conducted in this same age-range and community. Additionally, we will request that the primary caregiver accompany the child to the lab visit (i.e, spends at least 50% or more of total parenting time with the child). If interested in participating, caregivers will complete an additional phone screen to determine whether they meet any Coronavirus-specific exclusion criteria. This phone screen will assess whether participants may have contacted Coronavirus and whether they are at higher risk for severe illness. Any participants who do not pass this screening will not be permitted to take part in the study.

13.4 The flier that we plan to use for recruitment will be attached to this submission. It includes a picture of a minions stuffed animal with an EEG

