Certain persons are at higher risk for severe illness from Coronavirus, and these persons are not permitted to take part in our study. Persons thought to be at higher risk include:

- Being 65 years of age or older
- Prior or current exposure to persons that have Coronavirus whether or not they know it
- Persons of any age with serious medical conditions such as diabetes, and heart, lung, kidney or liver disease, or persons who are severely obese
- Persons who have poor immunity, such as persons under cancer treatment or who have other conditions with weakened immune systems

- People who reside in or have visited nursing homes or other long-term care facilities in the 14 days prior to the lab visit.
- People who have been experiencing or have been in contact with someone experiencing flu-like symptoms such as cough, low-grade fever or high temperature (100.4°F), shortness of breath, and/or difficulty breathing in the 14 days prior to the lab visit.
- Traveled outside of the Tallahassee area in the 14 days prior to the lab visit.

All participants and study personnel will therefore be asked some questions to see who may be at risk of severe illness, or who have been exposed to Coronavirus. Even after questions are asked, participants are strongly encouraged to inform research personnel if they think that at any time before or during the study they may been exposed to Coronavirus or are at risk of severe illness. Such participants will not be permitted to participate in this study. While the study staff will take steps to protect themselves and participants from exposure to Coronavirus when they take part in face-to-face activities, there is always the chance that an individual may still be exposed.

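### As worded, the day-of-visit COVID screen excludes a family from the study, not just from that visit, so at month 6 it would cost randomised dyads their Aim 2 ERN and Aim 3 anxiety outcomes

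*Combined protocol and SAP*

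**What the plan says.** **The screen and its consequence.** The COVID text in section 6.2 has two sets of questions. The first, at scheduling, concerns lasting high-risk conditions. The second concerns the family's travel, flu-like symptoms, contacts, and nursing-home or state-hospital visits in the past 14 days. Of the second set it says: "On the day of each in-person lab visit, subjects will be called and asked an additional series of screening questions". The consequence follows: "Individuals who meets these criteria will be excluded from participation in the study". Section 4.1 plans two lab visits, baseline and six months, so the sentence covers both.

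**The risk section.** Section 15.1 repeats the 14-day items and ties them to the lab visit. It asks participants to tell staff if they think that "at any time before or during the study they may been exposed to Coronavirus or are at risk of severe illness", and concludes: "Such participants will not be permitted to participate in this study".

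**The eligibility sections.** Section 10.2 places the phone screen before the in-lab visit and says: "Any participants who do not pass this screening will not be permitted to take part in the study". Section 13.3 introduces it this way: "If interested in participating, caregivers will complete an additional phone screen to determine whether they meet any Coronavirus-specific exclusion criteria". Both read as entry criteria.

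**Follow-up and withdrawal.** Section 6.2 also says: "We will also collect 6-month follow-up data in the lab for each parent/child dyad". Section 14.1 anticipates no withdrawal of subjects without their consent. Section 25.1 expects 90% retention, based on an earlier study at the same university, and does not mention COVID exclusions.

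**The concern.** One sentence does two different jobs. Before randomisation it decides who enters. At month 6 it applies to families who have been allocated and treated, and the trigger may be gone two weeks later. A coordinator who follows the text excludes the dyad; one who rebooks the visit departs from the text.

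What is at stake is the month-6 outcome. The ERN task, questionnaires, behavioural observation and interviews are all tied to the second lab visit (section 6.3). A dyad turned away for good therefore has no month-6 ERN for Aim 2 and no month-6 anxiety measure for Aim 3, on top of ordinary attrition. Aim 1 is complete after the first visit and is untouched. Aim 2c would keep some data, because section 5.0 says "we will periodically ask parents and children to complete the Error Sensitivity Index to track changes across the 6 months between lab assessments", but this sits within optional online modules and replaces neither the ERN nor the anxiety measures. The control arm has only 25 dyads, so each control lost matters most for precision.

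**Working it through.** **1. Order of events.** Consent is obtained at the start of the lab visit (section 22.1), and randomisation follows at that same visit (section 6.3, Procedure). The day-of-visit call comes before the family attends. So:

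- Baseline: call, consent, randomisation. A positive answer affects recruitment only.
- Month 6: randomisation, treatment, call. A positive answer affects a randomised dyad.

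**2. Search for a rebooking rule.** None appears in the visible COVID, procedure, withdrawal or timeline text. Section 6.3 places the second visit approximately six months after the first, which leaves room for rebooking but does not provide for it. The Coronavirus Information Sheet named in section 15.1 is not visible.

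**3. The plan's own retention figure.** Section 25.1 gives 90% retention, N = 155. Exactly, 0.90 × 175 = 157.5, and 155/175 = 88.6%, so the stated figure reproduces to within rounding. I start from 157.5: 0.90 × 150 = 135 active and 0.90 × 25 = 22.5 control.

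**4. Loss at month 6.** The documents give no screen-positive rate, so let f be an assumed share of otherwise retained dyads, applied to every month-6 visit.

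- Dyads lost = 157.5 × f
- Controls lost = 22.5 × f

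**5. Precision.** The documents state no alpha, power or effect size. I assume two-sided 0.05 and 80% power for pooled active versus control. The detectable effect d, in SD units, solves power = 0.80 for a two-sample noncentral t, with noncentrality d / √(1/n_active + 1/n_control) and n_active + n_control − 2 degrees of freedom.

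| f (assumed) | Retained | Lost | Controls left | Detectable effect | Change | Power at 0.642 SD |
|---|---|---|---|---|---|---|
| 0 | 157.5 | 0 | 22.5 | 0.642 | – | 80% |
| 5% | 149.6 | 7.9 | 21.4 | 0.659 | +2.6% | 78% |
| 10% | 141.8 | 15.8 | 20.3 | 0.677 | +5.5% | 76% |
| 20% | 126.0 | 31.5 | 18.0 | 0.719 | +12.0% | 71% |

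For one active arm (45 retained) against control, the same method gives 0.73 SD at f = 0, then 0.75, 0.78 and 0.82 SD.

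These are upper values for each f. If the measures covered only half of the month-6 visits, an assumed 20% would act like the 10% row (0.20 × 0.5 = 0.10).

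**6. Load if visits were rebooked.** Section 6.2 plans 6 dyads per month, so at 90% retention there are 6 × 0.9 = 5.4 month-6 visits per month. Multiplying by f gives 0.27, 0.54 and 1.08 rebooked visits per month, on top of 6 + 5.4 = 11.4 planned visits. Section 15.1 allows at most one lab visit per day, so this fits. Recruitment takes 175/6 = 29.2 months and the last month-6 visit falls near month 35.2 of the 36 in Years 2–4, with Year 5 available to complete follow-ups.

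**The case against.** The best reply is that this is loose wording added in a pandemic, not a plan to drop randomised families. Section 15.1 ties the 14-day items to the lab visit, so they lapse with time. Sections 10.2 and 13.3 treat the phone screen as an entry check, and staff would probably rebook. The intention may well have been a visit-level rule. But section 6.2 names each in-person visit and states the consequence as exclusion from the study, and section 15.1 extends this to exposure arising during the study. The stated rule, not only a missing detail, produces the loss.

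Four further points stand and limit the finding:

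- **The tension is not a strict contradiction.** Collecting month-6 data for each dyad is a plan that already coexists with 90% expected retention, and section 14.1 states an expectation about withdrawal.
- **A lost visit is not a discarded dyad.** A reader might infer that earlier data would be thrown away. No section says so; only the month-6 measures would be missing.
- **Lasting and transient criteria differ.** The section 15.1 sentence also covers people at risk of severe illness, for whom a later visit may never be possible. The point here concerns the transient 14-day items.
- **Unseen material.** The information sheet is not visible and consent pages were removed from the text reviewed. Rebooking instructions could be there.

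**Conclusion.** The point holds on the wording. Applied literally, the day-of-visit screen would take randomised dyads out of the month-6 lab outcomes for a temporary reason, and nothing visible provides for a later visit.

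The size is uncertain and probably modest. It rests on assumed screen-positive rates, an assumed alpha and power, and application of the screen to every month-6 visit. At 5–10% the pooled detectable effect worsens by about 0.02 to 0.04 SD. At 20% it worsens by about 0.08 SD (0.719 − 0.642), but nothing in the documents supports that rate in particular.

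A reader might infer that the exclusions would bias the comparison between arms. The documents do not support this: nothing in them suggests that travel, symptoms or contacts depend on allocation. The harm shown is loss of precision that can be avoided at little cost.

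**What to change.** Reconcile the day-of-visit exclusion sentence in section 6.2, and the sentence in section 15.1 on exposure during the study, with the follow-up plan in section 6.2 and the withdrawal statement in section 14.1. State the consequence at month 6 separately from the entry criterion:

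- Before randomisation, the screen remains an entry criterion. Sections 10.2 and 13.3 already read that way and need little or no change.
- After randomisation, a positive answer on a transient 14-day item should not by itself withdraw the dyad from follow-up or analysis. The month-6 visit can be held later if the site's rules permit, with the actual date recorded.
- Who may attend in person, and when, stays with the site's safety rules, including for lasting high-risk criteria. This review proposes no change to them.

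The cost is a sentence or two of protocol wording and roughly 0.3 to 1.1 rebooked visits per month at the assumed rates. The downside is a somewhat wider month-6 window, with slightly longer access to the online materials for rebooked dyads.
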